
Proprietary confidential information.

© 2019 Boehringer Ingelheim International GmbH or one or more of its affiliated companies. All rights reserved.

This document may not - in full or in part - be passed on, reproduced, published or otherwise used without prior written permission.

Name of company: Boehringer Ingelheim		Tabulated Trial Protocol	
Name of finished product: Not applicable			
Name of active ingredient: Dabigatran etexilate, BIBR 1048 MS			
Protocol date: 05 June 2013	Trial number: 1160.106		Revision date: 06 Feb 2019
Criteria for safety: 
 • Incidence of bleeding events including: 
 ○ Major bleeding events, clinically relevant non-major (CRNM) bleeding events, minor bleeding events and any bleeding events ○ Combined endpoint of major and CRNM bleeding events • Incidence of adverse events, protocol-specified AESIs and serious adverse events • Treatment discontinuation due to an adverse event • Change from baseline in safety laboratory values, vital signs and physical examination • Global assessment of tolerability (measured as treatment discontinuation and adherence) to study medication 			
Statistical methods: The primary efficacy endpoint will be tested for non-inferiority using non-inferiority margin of 20% at one-sided level of 0.05. Upon showing non-inferiority for the primary endpoint, superiority test for the primary endpoint will be performed subsequently at one-sided level of 0.05 without multiplicity correction. Mantel-Haenszel type weighted average of proportion difference, Kaplan-Meier method, Cox proportional hazard model, Logistic regression and descriptive statistics will be used in the planned analyses.			

Proprietary confidential information.

© 2019 Boehringer Ingelheim International GmbH or one or more of its affiliated companies. All rights reserved.

This document may not - in full or in part - be passed on, reproduced, published or otherwise used without prior written permission.

FLOW CHART

Trial Period	Screening	Treatment Period (open-label) with Dabigatran Etexilate (Dabi) or Standard Of Care (SOC)											Follow-up ^A	
		1 ^X	2	3 ^B	4	5 ^Y	6	7	8 ^C	Dabi Titration ^B Visit if needed ^B	INR/anti-Xa Visit if needed ^B	Unscheduled Visit if needed ^D		eEOT ^E Only for early discontinued patients (before Y8)
Visit (V) #:	1 ^X	2	3 ^B	4	5 ^Y	6	7	8 ^C						
Study week	-2	1	1	2	3	6	9	12						V8 or eEOT + 28 days

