- D. Unscheduled clinic visits are to be conducted in all cases of suspected symptomatic and asymptomatic VTE, progression/recurrence of VTE, paradoxical embolism (PDE), occurrence of post-thrombotic syndrome (PTS), major or clinically relevant bleeding events (MBEs / CRBEs) or other suspected significant AE or SAE. The unscheduled visit should be performed as soon as possible, preferably within 24 hours after the site first becomes aware of a suspected event. This visit should include all appropriate diagnostic procedures. If VTE progression/recurrence, PDE, PTS, MBEs, CRBEs are confirmed, the patient taking dabigatran etexilate is to be discontinued from the dabigatran etexilate treatment arm (eEOT visit to be performed as soon as possible), and an appropriate standard of care VTE treatment should be initiated per the investigator's discretion and/or local guidelines and the patient should be followed for the remainder of the study. If it is decided that a patient is to be discontinued from treatment due to an event, an eEOT visit should be conducted.
An unscheduled Visit is also to be performed in case a dabigatran etexilate dose adjustment is needed.
- E. The early End Of Treatment (eEOT) visit will be required for all patients who have taken a dose of dabigatran etexilate but failed to complete the full planned treatment observation period (completion of Visit 8). If feasible, this visit is also required for patients randomized to SOC should they decide to discontinue the trial or permanently stop SOC treatment for any reason. eEOT visit is not required if the SOC treatment is changed during the course of the trial.
- F. The informed consent (and if applicable assent) should be obtained per local legislations and guidelines from the patient's parent(s) or legal guardian and patient where applicable before any study procedures are performed. Should patients reach legal age during the trial they must personally sign and date the informed consent form as soon as possible and, at the latest, at the next visit
- G. Prior to start of therapy, all study inclusion and exclusion criteria must be checked to confirm patient eligibility.

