6.2.3 End of trial and follow-up period

Patients who complete the treatment period and are not enrolled into the secondary VTE prevention study (BI trial 1160.108) are to be followed at Visit 9. For the schedule of assessments and procedures to be done at the follow-up visit refer to the [Flow Chart](#).

All patients who prematurely discontinue study medication will be invited to perform an eEOT Visit and the follow-up Visit 9, taking place 28 days thereafter. Subsequently they will be followed-up preferably according to the remaining visit schedule until the end of the

Proprietary confidential information.

© 2019 Boehringer Ingelheim International GmbH or one or more of its affiliated companies. All rights reserved.

This document may not - in full or in part - be passed on, reproduced, published or otherwise used without prior written permission.

study. At these visits collection of AEs, outcome events (e.g. occurrence of PTS, VTE, bleeding events, etc.) and use of concomitant medication will be done.

Patients having switched from dabigatran etexilate to SOC are considered as having early discontinuation of dabigatran etexilate treatment. However, such patients will still remain in the trial and will be followed as per the visit schedule till the end of the study. Patients having switched from one SOC to another during the treatment period, are not considered as having early discontinuation of treatment and should remain in the treatment period and be followed as per the visit schedule till the end of the study.

Proprietary confidential information.

© 2019 Boehringer Ingelheim International GmbH or one or more of its affiliated companies. All rights reserved.

This document may not - in full or in part - be passed on, reproduced, published or otherwise used without prior written permission.

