With a total sample size of 141 patients and a 2:1 randomization to dabigatran and SOC, respectively, approximately 94 patients will be randomized to receive dabigatran and approximately 47 patients to receive SOC. The following simulation has been performed to consider the variability in the estimate of the complete thrombus resolution rate. Assuming the number of complete thrombus resolution follows binomial distribution with unknown probability of success, the estimates of the complete thrombus resolution rate are subject to the variability of this distribution. One hundred thousand binomial samples were generated

Proprietary confidential information.

© 2019 Boehringer Ingelheim International GmbH or one or more of its affiliated companies. All rights reserved.

This document may not - in full or in part - be passed on, reproduced, published or otherwise used without prior written permission.

for dabigatran arm and SOC arm, with 94 and 47 patients respectively. The lower bound of the 90% confidence interval was calculated for each simulation using:

$$\hat{p}_{dabi} - \hat{p}_{soc} - 1.64 \times \sqrt{\frac{\hat{p}_{dabi}(1 - \hat{p}_{dabi})}{94} + \frac{\hat{p}_{soc}(1 - \hat{p}_{soc})}{47}}$$

where, \hat{p}_{dabi} and \hat{p}_{soc} are point estimates of the complete thrombus resolution rates of dabigatran arm and stand of care arm from each simulation. Samples are generated from binomial distribution assuming the true complete thrombus resolution rates are p_{dabi} and p_{soc} , respectively. The proportions of the lower bound above the non-inferiority margin among the 100,000 simulations are provided in the table below, under various assumptions of binomial distributions.

Table 7.6: 2 Summary of power estimates for primary efficacy endpoint with a sample size of 141

Assumptions used in generating simulated samples	Power of 90% CI lower bound above the non-inferiority margin -20%
Superior assumption: $(p_{dabi}, p_{soc}) = (0.77, 0.72)$	95%
Non-inferior assumption: $(p_{dabi}, p_{soc}) = (0.72, 0.72)$	82%
Suboptimal assumption: $(p_{dabi}, p_{soc}) = (0.68, 0.72)$	63%
Extremely conservative but non-inferior assumption: $(p_{dabi}, p_{soc}) = (0.62, 0.72)$	33%
Inferior assumption: $(p_{dabi}, p_{soc}) = (0.52, 0.72)$	5% (false positive)

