Under the assumption that the true unknown complete thrombus resolution rate is 72% of both dabigatran and SOC, the proposed sample size of 141 is sufficient to demonstrate non-inferiority with adequate power (82%).

If the complete thrombus resolution rate in dabigatran is truly lower than the SOC, the chance of showing non-inferiority drops to 33% when the difference is 10% (complete thrombus resolution rate 62% vs 72% for dabigatran and SOC, respectively), and to below 5% when the non-inferiority margin of 20% is reached (complete thrombus resolution rate 52% vs 72% for dabigatran and SOC, respectively).

However, the most likely scenario for the paediatric population is to assume similar thrombus resolution rates with both dabigatran and SOC, based on the following considerations: primary efficacy results obtained from adult VTE RE-COVER-trials ([P13-16985](#)) demonstrated robust non-inferiority. In addition, it is the expectation that the gMean trough concentration in the paediatric trials will exceed the average trough exposure of RE-COVER due to the option of up-titration of the dose if initial exposure is < 50 ng/ml compared to fixed dosing in the adult trials. Therefore the Sponsor considers the sample size and 20% margin are reasonably sensitive to evaluate non-inferiority in the paediatric population. See Table 7.6: 3 for summary.

Proprietary confidential information.

© 2019 Boehringer Ingelheim International GmbH or one or more of its affiliated companies. All rights reserved.

This document may not - in full or in part - be passed on, reproduced, published or otherwise used without prior written permission.

Table 7.6: 3 Summary of power estimates for the primary endpoint with a sample size of 141

One-sided confidence level	Primary endpoints (non-event rate)	True rate difference	Margin for rate difference	Power [#]
90%	72%	0.0%	20%	82%
95%	72%	0.0%	20%	71%

[#] Power for the non-inferiority approach is computed as the proportion of 100,000 simulations in which the observed upper bound of one-sided confidence intervals for $p_{1C} - p_{1D}$ and $p_{2C} - p_{2D}$ (assuming 94 and 47 evaluable patients in dabigatran arm and control arm, respectively) are below the specified equivalence margin. The confidence interval for the VTE endpoint is estimated by Newcombe-Wilson method ([R08-4386](#)).

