2. Given minimized risk of not detecting recurrent VTE due to the study design, as well as the low incidence rate of recurrent VTE in the study population, we assume patients free from recurrent VTE until the presence of contradictory evidence - observed VTE recurrence.

Component 3: complete thrombus resolution

Assessment of index VTE status (best overall response) is scheduled on Day 84 ± 7 days (Visit 8) for patients who are alive without an early consent withdraw, regardless of the treatment status (completion or premature discontinuation) at that time.

- The thrombus status assessed at Day 84 ± 7 days will be used for evaluation of this component. If more than one thrombus assessment is available within this time window, the one closest to Day 84 will be adopted. Furthermore, if two index assessments performed within the time window were equally distant from Day 84 (e.g., an early assessment on Day 78 and a late assessment on Day 90), then the thrombus status after Day 84 will be adopted.
- For patients completing the treatment period OR patients terminating treatment early, if the index thrombus assessment during Day 84 ± 7 days is missing, but an early VTE assessment was performed, for instance, at an unscheduled visit or an eEOT visit, the latest available thrombus status will be carried forward (LOCF) in the primary analysis.
- If not any index VTE assessment was performed until Day 84 + 7 days, these patients will be considered as having missing data and NOT meeting the criterion of “complete thrombus resolution”.
- Patients with index VTE assessment performed only once after Day 84 + 7 days will be considered to have missing data and to not achieve the complete thrombus resolution in the primary analysis,

Age group will be used as stratification factor using a Mantel-Haenszel type weighted average of differences with weights as proposed by Greenland and Robins [R09-1299] (3).

The testing hypotheses for the non-inferiority and superiority of the primary endpoint are:

$H_{01}: p_{IC} - p_{ID} \geq 20\%$ vs. $H_{11}: p_{IC} - p_{ID} < 20\%$, where p stands for the proportion of patients meeting the primary endpoint, the subscript C for SOC, and D for dabigatran etexilate.

$H_{03}: p_{IC} - p_{ID} \geq 0$ vs. $H_{13}: p_{IC} - p_{ID} < 0$.

The details of Cochran-Mantel-Haenszel test and SAS code are provided in [Section 9.4](#).

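### The early end-of-treatment visit, the only scheduled fallback for the thrombus image, is required for dosed dabigatran patients but conditional for SOC; because no image counts as failure, this risks arm-dependent ascertainment of the primary endpoint

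*Protocol*

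**What the plan says.** **Duty to attend.** Footnote E of the Protocol Flow Chart says that the eEOT "visit will be required for all patients who have taken a dose of dabigatran etexilate" and did not complete the planned period to Visit 8. For SOC the duty is conditional: "If feasible, this visit is also required for patients randomized to SOC should they decide to discontinue the trial or permanently stop SOC treatment". Section 3.3.4.1 covers patients who will not follow the remaining schedule but have not withdrawn consent, and provides only for a dabigatran eEOT visit. Section 6.2.3 makes no distinction by arm: "All patients who prematurely discontinue study medication will be invited to perform an eEOT Visit".

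**Role of the visit.** The Flow Chart places the thrombus extension assessment at screening, Visit 8 and eEOT only. Protocol Section 7.4 names the eEOT observation as the value carried forward when the Visit 8 assessment is missing. SAP Section 7.4 (Component 3) takes the image in the Day 84 ± 7 window first. If there is none but an earlier assessment exists, for instance from an unscheduled or eEOT visit, then "the latest available thrombus status will be carried forward (LOCF) in the primary analysis". A patient with no index assessment up to Day 84 + 7 is treated as not having complete resolution.

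**Test.** "The primary efficacy endpoint will be tested for non-inferiority using non-inferiority margin of 20% at one-sided level of 0.05"

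**The concern.** The plan's own rules give the two arms different chances of having a fallback image, and they convert the absence of an image into a failure. In a non-inferiority trial, failures added to the control arm move the estimate towards the conclusion sought. Treatment is open-label, and blinded adjudication cannot recover an image that was never taken. With about 47 SOC patients, one patient is about 2% of the arm, so one or two missing images are enough to matter. Sites also cannot tell whether footnote E or Section 6.2.3 governs an SOC patient who stops early.

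**Working it through.** **Inputs from the documents**
- Margin 20 percentage points, one-sided 0.05, assessed with a 90% interval (Protocol synopsis and Section 7.2).
- Arm sizes: "approximately 94 patients will be randomized to receive dabigatran and approximately 47 patients to receive SOC" (Protocol Section 7.6).
- Planning rate: "Under the assumption that the true unknown complete thrombus resolution rate is 72% of both dabigatran and SOC" (Protocol Section 7.6).
- Decision rule (Protocol Section 7.6): declare non-inferiority if p_D − p_C − 1.64·√[p_D(1−p_D)/94 + p_C(1−p_C)/47] > −0.20, where p_D and p_C are the observed dabigatran and SOC rates.

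**Step 1: reproduce the plan's figures.** Exact binomial enumeration of that rule, with SOC at 72%:

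| True dabigatran rate | Stated | Computed |
|---|---|---|
| 77% | 95% | 95.2% |
| 72% | 82% | 81.8% |
| 68% | 63% | 63.3% |
| 62% | 33% | 32.3% |
| 52% (at the margin) | 5% | 4.7% |

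The enumeration matches Table 7.6: 2 to within a percentage point. The baseline false-positive rate used below is 4.7%.

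**Step 2: excess loss of SOC images.** Let m be the excess share of SOC patients with no image by Day 84 + 7, and q the share of those lost images that would have shown resolution. The observed SOC rate becomes 0.72 − m·q. Neither m nor q is given in the documents, so both are assumptions. Dabigatran loss is set to zero and the dabigatran rate to 52%.

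| m (patients of 47) | q | SOC rate | False-positive rate |
|---|---|---|---|
| 2% (0.9) | 0.20 | 0.72 − 0.0040 = 0.7160 | 5.2% |
| 2% | 0.50 | 0.72 − 0.0100 = 0.7100 | 6.1% |
| 2% | 0.72 | 0.72 − 0.0144 = 0.7056 | 6.7% |
| 5% (2.4) | 0.20 | 0.72 − 0.0100 = 0.7100 | 6.1% |
| 5% | 0.50 | 0.72 − 0.0250 = 0.6950 | 8.6% |
| 5% | 0.72 | 0.72 − 0.0360 = 0.6840 | 10.9% |

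The upper value of q treats lost images as typical of the SOC arm. The lower value allows for patients who stop because the clot has resolved having been imaged already.

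**Step 3: equal loss.** If 5% of each arm had no image, regardless of outcome, the rates would be 0.52 × 0.95 = 0.494 and 0.72 × 0.95 = 0.684. The false-positive rate is then 6.3%, and power with 72% in both arms is 78.8%. Equal duties remove the tilt between arms but not the effect of scoring missing images as failures.

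**Step 4: a force in the other direction.** Protocol Section 7.6 allows for up to 15% discontinuation on dabigatran. Suppose that 15% stop, half of them have only an early eEOT image, and the success rate on those early images is half as high. The dabigatran rate falls by the factor 1 − 0.15 × 0.5 × 0.5 = 0.9625, so 52% becomes 50.05%. Combined with SOC loss at q = 0.72, the false-positive rate is 4.3% for m = 2% and 7.3% for m = 5%.

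All steps use the unstratified interval of Section 7.6, not the age-stratified estimator of the primary analysis, so they show scale only.

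**The case against.** A reader might infer that SOC will lose successes and that the trial is therefore biased towards dabigatran. The documents do not support that.

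- Visit 8 imaging is scheduled in both arms whatever the treatment status (SAP Section 7.4), and footnote J asks early stoppers to complete Visits 8 and 9 at minimum, though as a preference.
- Patients who stop because the thrombus has resolved have been imaged and have an early EOT visit in either arm (Section 3.3.4.1). Footnote D calls for an eEOT visit after any stop due to an event. SOC patients who change SOC type stay on schedule.
- Unscheduled images also count. After withdrawal of consent, no visit can be required in either arm.
- Dabigatran has additional protocol-driven stops, such as a trough level out of range after one adjustment. An early image carried forward may score a slowly resolving dabigatran patient as a failure.
- Footnote E's firm duty covers only dosed dabigatran patients, whereas the randomised set also includes undosed ones.

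These points stand. Harm requires an SOC patient with no Visit 8, eEOT or unscheduled image, and this must happen more often than on dabigatran. It is also too strong to call footnote E and Section 6.2.3 contradictory: an invitation and a conditional requirement can both be followed, though they set different standards. What remains is that the plan words the fallback duty differently by arm, that Section 3.3.4.1 repeats the difference, and that nothing ensures the opposing forces cancel.

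Nor can one infer that the SAP lacks a suitable sensitivity analysis. Table 6.3: 1 mentions one on the treated set, and some SAP sections are missing from the copy reviewed.

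**Conclusion.** The concern holds as a risk of arm-dependent ascertainment, of uncertain net direction. If SOC images are lost in excess and dabigatran images are not, the false-positive rate at the margin (52% v 72%, 94 and 47 patients) rises from 4.7% to 5.2-6.7% for a 2% excess and to 6.1-10.9% for a 5% excess, with 20-72% of lost images assumed resolved. With the assumed offset from early dabigatran images, a 2% excess gives 4.3%, slightly below baseline. The loss rates, the resolved share and the offset are all assumptions. The unequal duty and the rule that no image is a failure are in the documents. The change is worth making because it is cheap and removes a difference between arms that serves no stated purpose.

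**What to change.** **Protocol.** Reconcile footnote E and Section 3.3.4.1 with Section 6.2.3, so that any randomised patient in either arm who permanently stops treatment or leaves before Visit 8 has the same requirement for an eEOT visit with index-thrombus imaging, consent permitting.

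**SAP.** Tabulate by arm how many primary outcomes rest on a Day 84 window image, on a carried-forward image and on no image. If not already planned in the sections missing from this copy, add one sensitivity analysis that does not score missing images as failures and that states how they are handled. Restricting the analysis to Day 84 window images would not be enough without that statement: scoring the gaps as failures adds failures, and dropping those patients departs from intention to treat.

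**Cost.** Wording changes, a few SOC visits with imaging already in the Flow Chart, one table and, if needed, one additional analysis.

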CRNM	Clinically relevant non-major (bleeding)
CRO	Contract Research Organisation
CTMF	Clinical Trial Master File
CTP	Clinical Trial Protocol
CTR	Clinical Trial Report
CT	Computed Tomography
CVL	Central venous Line
DILI	Drug-Induced Liver Injury
DMC	Data Monitoring Committee
dTT	Diluted Thrombin Time
DVT	Deep venous thrombosis
EC	Ethics Committee
ECG	Electrocardiogram
ECT	Ecarin clotting time
EDTA	Ethylenediaminetetraacetic acid
eGFR	Estimated Glomerular Filtration Rate
EU SPC	European Union Summary of Product Characteristics
EOT	End of Treatment
eEOT	Early End of Treatment
F	Fahrenheit
FIIA	Factor IIA (synonym for thrombin)
FAS	Full Analysis Set
FDA	Food and Drug Administration

Proprietary confidential information.

© 2019 Boehringer Ingelheim International GmbH or one or more of its affiliated companies. All rights reserved.

This document may not - in full or in part - be passed on, reproduced, published or otherwise used without prior written permission.

FEIBA	Factor Eight Inhibitor Bypassing Activity
FRAC	Fraction of Adult Dose
GCP	Good Clinical Practice
h	Hour
HPLC	High Pressure Liquid Chromatography
ICF	Informed Consent Form
ICH	International Conference on Harmonisation
IEC	Independent Ethics Committee
INR	International Normalized Ratio
IRT	Interactive Response Technology
ISF	Investigator Site File
ISTH	International Society on Thrombosis and Haemostasis
IRB	Institutional Review Board
IUD	Intra-Uterine Device
IVRS / IWRS	Interactive Voice Response System / Interactive Web Response System
LMWH	Low Molecular Weight Heparin
MedDRA	Medical Dictionary for Regulatory Activities
mL	Millilitre
mg	Milligram
MRI	Magnetic Resonance Imaging
MS	Mass Spectrometry
Na	Sodium
ng	Nanogram
No.	Number
OAC	Oral anticoagulant
OLF	Oral Liquid Formulation
OPU	Operative Unit (of BI)
PE	Pulmonary embolism
PD	Pharmacodynamic
PDCO	Paediatric Committee (of the European Medicines Agency)
PK	Pharmacokinetic
PKS	Pharmacokinetic Set
PPI	Proton Pump Inhibitor
PT	Prothrombin Time
PTS	Post Thrombotic Syndrome
SAE	Serious Adverse Event
SGOT	Serum Glutamic Oxaloacetic Transaminase
SGPT	Serum Glutamate Pyruvate Transaminase
SI	International System of Units
SOC	Standard of Care
SOP	Standard Operating Procedure
SPAF	Stroke Prevention in Atrial Fibrillation
SUSAR	Suspected Unexpected Serious Adverse Reaction
sVTEp	Secondary Venous thromboembolism Prevention
t _{1/2}	Terminal Half-Life
TDMAP	Trial Data Management and Analysis Plan

Proprietary confidential information.

© 2019 Boehringer Ingelheim International GmbH or one or more of its affiliated companies. All rights reserved.

This document may not - in full or in part - be passed on, reproduced, published or otherwise used without prior written permission.

t_{\max}	Time From Dosing to Maximum Measured Concentration
THR	Total hip replacement
TS	Treated Set
TSAP	Trial Statistical Analysis Plan
TT	Thrombin Time
UFH	Unfractionated Heparin
ULN	Upper Limit of Normal
VKA	Vitamin K Antagonist
VTE	Venous thrombotic event/Venous Thromboembolism
W	Weight

Proprietary confidential information.

© 2019 Boehringer Ingelheim International GmbH or one or more of its affiliated companies. All rights reserved.

This document may not - in full or in part - be passed on, reproduced, published or otherwise used without prior written permission.

